9.3. Vital Signs

Vital signs (temperature, heart rate, systolic blood pressure (SBP), diastolic blood pressure (DBP)) will be summarized using descriptive statistics (sample size, mean, SD, median, minimum, and maximum) at baseline and at each post-baseline time point by treatment. Change from baseline will also be summarized at each post-baseline time point. Mean (+/- SD) vital sign values will be graphically presented over time by treatment. All vital signs results will be listed.

9.4. ECG Results

Shift from baseline in 12-Lead ECG overall interpretation (results are Normal, Abnormal Not Clinically Significant (NCS), or Abnormal Clinically Significant (CS)) will be summarized at each post-baseline study day by treatment. Mean (+/- SD) continuous ECG parameter values will be graphically presented over time by treatment.

Additionally, the number and percentage of subjects will be summarized for the following QTcF Interval result categories at baseline and study day 15 by treatment:

- <=450 msec (males) or <=470 msec (females)
- >450 msec (males) or >470 msec (females)

CONFIDENTIAL Page 15 03DEC2021

- Change from baseline <=60 msec (only applies to post-baseline visits)
- Change from baseline >60 msec (only applies to post-baseline visits)

A listing of ECG results will present the interpretations of abnormalities and whether these are considered clinically significant by the investigator.

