^e Procalcitonin: record only initial measurement or within 48 hours of admission and/or SARS-CoV-2 diagnosis (may be performed prior to date of enrollment) ^f Record maximal daily level of O₂ by nasal cannula prescribed, if applicable

⁹ Record maximal daily level of end expiratory pressure delivered by CPAP prescribed, if applicable

^h Record maximal daily level of PEEP and delivered FiO₂ by mechanical ventilation, if applicable

¹ Study drug administration will commence on the day of enrollment if treatment can be administered before 10 pm and then with AM medications thereafter, If, study drug cannot be administered prior to 10 pm on the day of enrollment, then the 1st day of treatment will occur on the day after enrollment.

¹ Perform a 12-lead ECG on the 2nd day of treatment with study drug between 75 and 90 minutes post-administration on day 2; and on day 15 (± 2 days)

^k Serum is collected for CPK and GGT on day 1 and day 7, and weekly thereafter, if values on day 7 are abnormal until return to normal

¹ PK assessment will be performed for the initial 15 subjects enrolled. Blood (5 ml) will be collected for plasma collection at baseline (pre-treatment), and then at 1, 2, 4, and 8 hr. Trough measurements will be obtained as indicated for all study participants

^m The clinical record should be reviewed through to Day 56 as relevant to denote date of discharge, date of death, or clinical status (WHO COVID-19 Classification Level) at Day 56

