>450 msec (males) or >470 msec (females)	xx (xx.x)	xx (xx.x)	xx (xx.x)	xx (xx.x)
Change from baseline <=60 msec	xx (xx.x)	xx (xx.x)	xx (xx.x)	xx (xx.x)
Change from baseline >60 msec	xx (xx.x)	xx (xx.x)	xx (xx.x)	xx (xx.x)

Baseline is the last non-missing value prior to first dose of study treatment.

Percentages are based on n, the number of subjects with a baseline and post-baseline (for Week 4) result at the study day.

Reference: Listing 16.2.8.4

time date

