APPENDIX D: FIGURE LAYOUTS

Protocol: GLS27-005

Figure 14.2.2.1

Line Plot of Mean (+/- SD) PEEP Results During Intubation by Study Day (ITT Population)

Figure 14.2.2.2 Line Plot of Mean (+/- SD) PEEP Results During Intubation by Study Day (PP Population)

Figure 14.3.4.1

Line Plots of Mean (+/-SD) Vital Sign Results by Test and Study Day (Safety Population)

Figure 14.3.4.2

Line Plots of Mean (+/-SD) 12-Lead ECG Results by Test and Study Day (Safety Population)

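### The SAP gives no table or estimate of mean QTcF change against placebo: QTcF is tabulated only by category, and arm means appear only in a plot of observed values

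*SAP*

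**What the plan says.** SAP 9.4 plans three displays of ECG data. The first is a shift table of the overall interpretation. The second is a count table for QTcF, introduced by the sentence that "the number and percentage of subjects will be summarized for the following QTcF Interval result categories at baseline and study day 15 by treatment". Its rows are the sex-specific absolute cut (450 or 470 msec) and change from baseline of at most 60 msec or above it. The third is a plot of mean and SD of continuous ECG parameters over time by treatment.

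The shell of Table 14.3.4.6.2 in Appendix C repeats these rows, including "Change from baseline >60 msec", for Day 2 as well as Day 15. Every entry is a count and a percentage. The figure in Appendix D is titled "Line Plots of Mean (+/-SD) 12-Lead ECG Results by Test and Study Day"; neither the title nor the text names QTcF among the parameters plotted. Listing 16.2.8.4 lists individual ECG results. The Appendix B index has no other ECG table.

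The ECG with a fixed time after dosing is the Day 2 one. The Schedule of Events footnote in protocol Table S2 reads "Perform a 12-lead ECG on the 2nd day of treatment with study drug between 75 and 90 minutes post-administration on day 2". Protocol 6.2.3.5 has the baseline or first ECG of the admission recorded.

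Other safety variables are handled differently. SAP 9.3 summarizes change from baseline in vital signs as a continuous variable at each time point, and the shells of Tables 14.3.4.1 and 14.3.4.2 do the same for laboratory tests.

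**The concern.** To place a patient above or below 60 msec, the programmer must already hold that patient's baseline and post-dose QTcF. The plan then keeps one bit of that difference. A change above 60 msec is an extreme individual event, and with about 44 patients per arm very few would be expected even if the whole arm had shifted moderately. A table reading 0 against 1, or 1 against 2, says little about whether the arm mean has moved.

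Protocol 7.3 lists changes in ECGs among the safety assessments, and the trial compares two doses with placebo. At the end, a reader would want to know how far mean QTcF moved at each dose relative to placebo and how precisely that is known. No planned table answers this, and the SAP gives no reason for treating ECG data differently from vital signs and laboratory tests.

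**Working it through.** **The plan's own figure.** There is none to reproduce. The documents state no QTcF effect, SD, expected count or power.

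**Inputs.** From the documents: the 60 msec cut and the 450/470 msec cut (SAP 9.4), and 44 patients per group (SAP 4). Assumed: QTcF change is normal with mean 0 on placebo and SD 15-30 msec, the mean shift on active drug is 10 or 20 msec, and all 44 patients per arm have paired ECGs.

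**Formulas.**
- P(change > 60) = 1 − Φ((60 − shift)/SD), and expected count = 44 × P. Example, SD 20 and shift 10: (60 − 10)/20 = 2.5, P = 0.0062, count 0.27. With no shift: 60/20 = 3, P = 0.00135, count 0.06.
- Power of the above-60 row: exact enumeration of the two-sided Fisher test, 44 v 44, alpha 0.05.
- Power for mean change: two-sample t test with noncentrality shift/(SD × √(2/44)). Example, SD 20 and shift 10: 10/(20 × 0.213) = 2.35, power 64%.
- 95% CI half-width = t(0.975, 86 df) × SD × √(2/44). Example, SD 20: 1.988 × 20 × 0.213 = 8.5 msec.

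| SD (msec) | Expected > 60 of 44: shift 0 / 10 / 20 | Power, > 60 row: +10 / +20 | Power, mean change: +10 / +20 | CI half-width (msec) |
|---|---|---|---|---|
| 15 | 0.00 / 0.02 / 0.17 | <0.1% / <0.1% | 87% / >99% | 6.4 |
| 20 | 0.06 / 0.27 / 1.0 | <0.1% / <0.1% | 64% / >99% | 8.5 |
| 25 | 0.36 / 1.0 / 2.4 | <0.1% / 2.3% | 46% / 96% | 10.6 |
| 30 | 1.0 / 2.1 / 4.0 | 0.7% / 9.5% | 34% / 87% | 12.7 |

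The reason is visible in the counts. If placebo has none above 60 msec, 6 of 44 on active drug are needed for a two-sided p below 0.05: 2 × C(44,6)/C(88,6) = 0.026, whereas 5 of 44 gives 0.055. The expected count reaches 4 only in the most variable case with the larger shift.

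Fewer paired ECGs do not change the picture. At 35 per arm, SD 20 and a shift of 10, the comparison is below 1% against 54%.

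**The absolute cut.** This needs further assumptions. Take observed QTcF as normal, with placebo mean 415-435 msec and SD 20-30 msec, and apply the 450 cut to everyone. For +20 msec, the expected number above the cut rises from 1.8-13.6 to 10-26 of 44, and Fisher power is 47-93%. For +10 msec, power is 9-34%. With half women, the 470 cut applied to them, mean 410-430 in men and 10 msec higher in women, the ranges are 24-85% for +20 and 1-23% for +10. This row may therefore register a larger shift, but it remains a count.

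**The case against.** A reader might infer that a 10-20 msec prolongation would go unseen and be reported as no signal. The documents do not support that. The same section plots arm means by treatment, and in a randomized comparison the difference between arm means at Day 2 estimates the effect without pairing. Since SD(change) = SD(observed) × √(2(1 − ρ)), pairing adds precision only if the correlation between the two ECGs exceeds 0.5, and the documents give no correlation. If QTcF is among the plotted parameters, a separation would be displayed. The absolute cut, as shown above, may also react to 20 msec. What is missing is an estimate with an interval, not every sight of the mean.

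Three further limits stand. The primary safety objective is the incidence of serious adverse events, so QTcF is supporting safety data. A reader might take the Day 2 ECG to be near peak exposure, but the protocol gives Cmax, AUC and half-life without a time of peak and does not say why 75-90 minutes was chosen. No test on safety data is planned, so the Fisher and t comparisons are yardsticks for information and do not describe a test that the trial would fail. A baseline-adjusted contrast also goes beyond what this SAP does for any other safety variable.

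The objection does not close the gap. The plot shows observed values with SD bars. It gives no paired change, no difference from placebo and no CI, and SD bars describe spread between patients, not uncertainty in the mean. Tabulating continuous change would only bring ECG data level with vital signs and laboratory tests.

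**Conclusion.** The point holds as a gap in the safety tables. SAP 9.4 and Table 14.3.4.6.2 yield no tabulated mean QTcF change and no estimate against placebo. The row meant to capture change is nearly blind to a 10-20 msec mean shift under every SD assumed, while the paired values needed for a better summary are already required to derive it. The size rests on the assumed SD of 15-30 msec, normality and 44 paired ECGs per arm. The figures for the absolute cut rest on assumed baseline distributions as well. Nothing here suggests that the drug prolongs QT, and neither the primary efficacy analysis nor the primary safety analysis is affected. The change should be made before unblinding.

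**What to change.** In SAP 9.4 and Table 14.3.4.6.2, keep the existing categories. For each post-baseline ECG (Day 2 post-dose and Day 15), add n, mean and SD of QTcF change from baseline, and the difference of each dose from placebo adjusted for baseline QTcF, with a 95% CI. Label the block descriptive. Name QTcF explicitly among the parameters in Figure 14.3.4.2.

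In the same edit, reconcile the 9.4 sentence, which names only baseline and Day 15, with the shell, which also has Day 2. Correct the table footnote that refers to Week 4, which is not a visit in that table. A further split of the change category at 30 msec is optional and not needed for this point.

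The cost is a few more rows to program in an existing table. No new data are collected and no patient procedure changes.

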9.5. Physical Exam

Physical exam findings will be listed.

9.6. Urine Pregnancy Test

Pregnancy test results will be listed.

9.7. Other Data

Chest x-ray scores, nasal oxygen (O₂) administration and flow rate, and CPAP usage and PEEP, % FiO2 if mechanically ventilated, ECMO treatment will be presented in listings. The number of days of nasal oxygen (O₂) administration and flow rate, level of PEEP, % of FiO2 if mechanically ventilated, ECMO treatment and CPAP usage, will be summarized by treatment using descriptive statistics (sample size, mean, median, SD, minimum, maximum).

CONFIDENTIAL Page 16 03DEC2021

APPENDIX A: PRESENTATION OF DATA AND PROGRAMMING SPECIFICATIONS

Tables

- Formal organization of tabulations may be changed during programming if appropriate, e.g., tables for the different variables may be combined into a single table, or tables with more than one variable may be split into several tables.
- Means and medians will be presented to one more decimal place than the raw data. SDs will be presented to two more decimal places than the raw data. Minimums and maximums will be reported with the same number of decimal places as the raw data.
- Percentages will be presented to the tenths place.
- For frequency counts of categorical variables, categories whose counts are zero will be displayed for the sake of completeness. For example, if none of the subjects discontinue due to "lost to follow-up," this reason will be included in the table with a count of 0. Categories with zero counts will not have zero percentages displayed.
- The last footnote will be "Reference: xxx", where xxx indicates the source listing number(s).

Listings

- Formal organization of the listing may be changed during programming if appropriate, e.g., additional variables may be included, change in the column order, or the listing may be split into multiple parts due to space constraints, etc.
- If not otherwise specified, all data listings will be sorted by treatment, subject number, visit, and date/time as appropriate.
- All date values will be presented in an ISO 8601 date (e.g., 2001-08-29) format.
- All observed time values will be presented using a 24-hour clock HH:MM:SS format (e.g., 01:35:45 or 11:26). Seconds will only be reported if they were measured as part of the study.

Missing or incomplete dates, i.e., AEs and concomitant medications

The most conservative approach will be systematically considered. If the AE onset date is missing or incomplete, it is assumed to have occurred during the study treatment phase (i.e., considered a TEAE) except if the partial onset date or other data such as the stop date, indicates differently. Similarly, a medication with partial start and stop dates could be considered as a concomitant treatment.

The following algorithms will be applied to missing and incomplete start and stop dates:

Start Dates

- If the day portion of the start date is missing, then the start date will be estimated to be equal to the date of IP administration, provided the start month and year are the same as IP administration and the stop date is either after IP administration or completely missing. Otherwise, the missing day portion will be estimated as '01'.
- If both the day and month portions of the start date are missing, then the start date will be estimated to be equal to the date of IP administration, provided the start year is the same as IP administration and the stop date is either after IP administration or completely

CONFIDENTIAL Page 17 03DEC2021

- missing. Otherwise, the event will be assumed to start on the first day of the given year, e.g., 2013-??-?? is estimated as 2013-01-01.
- If the start date is completely missing and the stop date is either after IP administration or completely missing, the start date will be estimated to be the day of IP administration. Otherwise, the start date will be estimated to be the first day of the same year as the stop date. All other non-AE and non-concomitant medication day calculations where only partial dates are available will be handled as follows: the first day of the month will be used in the calculations if the day part of a start date is missing while January 1 will be employed if both the month and day parts of a start date are missing.

Stop Dates

- If only the day of resolution is unknown, the day will be assumed to be the last of the month, e.g., 2013-01-?? will be treated as 2013-01-31.
- If both the day and month of resolution are unknown, the event will be assumed to have ceased on the last day of the year, e.g., 2013-??-?? will be treated as 2013-12-31.
- If the stop date is completely missing or the event is continuing, the event will be assumed to be after IP administration and will be left as missing.

Standard Calculations

Variables requiring calculation will be derived using the following formulas:

- Days A duration expressed in days between two dates (start date and end date) is calculated using the formulas noted below:
- duration in days = end date start date + 1, where end date \ge treatment start date
- duration in days = end date start date, where end date < treatment start date
- Months A duration expressed in months is calculated as the number days divided by 365.25/12 (~30.4).
- Years A duration expressed in years between one date (date1) and another later date (date2) is calculated using the formula: duration in years = (date2-date1+1)/365.25
- Height Height entries made in inches (in) are converted to centimeters (cm) using the following formula: height (cm) = height (in) $\times 2.54$
- Weight Weight entries made in pounds (lb.) are converted to kilograms (kg) using the following formula: weight (kg) = weight (lb.) / 2.2046
- Temperature Temperature entries in degrees Fahrenheit are converted to degrees centigrade using the following formula: temp (degrees centigrade) = 5/9 × [temp (degrees Fahrenheit) 32]

CONFIDENTIAL Page 18 03DEC2021

- Change from baseline Change from baseline will be calculated as: Change = post baseline value baseline value
- Percent change from baseline Change from baseline will be calculated as: percent change from baseline = post baseline value – baseline value / baseline value × 100

CONFIDENTIAL Page 19 03DEC2021

APPENDIX C: TABLE LAYOUTS

Table 14.1.1.1
Subject Disposition
(All Subjects)

Subject Status	GLS-1027	GLS-1027	Placebo	0verall
	120 mg	360 mg		
Screened				xx
Screen Failure				XX
ITT Population [1]	XX	XX	XX	XX
mITT Population [2]	xx	XX	XX	xx
Safety Population [3]	x (xx.x%)	x (xx.x%)	x (xx.x%)	x (xx.x%)
PP Population [4]	x (xx.x%)	x (xx.x%)	x (xx.x%)	x (xx.x%)
Completed the study	x (xx.x%)	x (xx.x%)	x (xx.x%)	x (xx.x%)
Discontinued the study	x (xx.x%)	x (xx.x%)	x (xx.x%)	x (xx.x%)
Reason for discontinuation	, ,	, ,	, ,	, ,
<reason #1=""></reason>	x (xx.x%)	x (xx.x%)	x (xx.x%)	x (xx.x%)
<reason #2=""></reason>	x (xx.x%)	x (xx.x%)	x (xx.x%)	x (xx.x%)
<reason #3=""></reason>	x (xx.x%)	x (xx.x%)	x (xx.x%)	x (xx.x%)

Percentages are based on the ITT Population, unless otherwise noted.

Reference: Listing 16.2.1

^[1] The Intent-to-treat (ITT) Population includes all randomized to treatment allocation.

^[2] The modified intention to treatment (mITT) population includes all participants who are randomized to a treatment allocation, and who have received at least one dose of study drug.

^[3] The Safety Population includes all subjects in the ITT population who received at least one dose of study drug.

^[4] The PP Population includes all safety subjects who complete the trial by meeting the endpoint or being discharged within 14 days without meeting the endpoint.

GeneOne Life Science Inc.

Page 1 of 1

Protocol: GLS27-005

Table 14.1.1.2
Reason for Screen Failure
(All Screen Failure Subjects)

Reason	Overall (xx)
<reason #1=""></reason>	x (xx.x%)
<reason #2=""></reason>	x (xx.x%)
<reason #3=""></reason>	x (xx.x%)

Reference: Listing 16.2.3

Table 14.1.2

Demographic and Baseline Characteristics
(ITT Population)

Characteristic	GLS-1027	GLS-1027		
	120 mg	360 mg	Placebo	Overall
	(N=XX)	(N=XX)	(N=XX)	(N=XX)
Age (years)				
n	xx	XX	xx	XX
Mean (SD)	xx.x (xx.xx)	xx.x (xx.xx)	xx.x (xx.xx)	xx.x (xx.xx)
Median	xx.x	xx.x	xx.x	xx.x
Min, Max	XX, XX	xx, xx	XX, XX	xx, xx
<65 years	x (xx.x%)	x (xx.x%)	x (xx.x%)	x (xx.x%)
>=65 years	x (xx.x%)	x (xx.x%)	x (xx.x%)	x (xx.x%)
Sex				
Male	x (xx.x%)	x (xx.x%)	x (xx.x%)	x (xx.x%)
Female	x (xx.x%)	x (xx.x%)	x (xx.x%)	x (xx.x%)
Race				
American Indian or Alaskan Native	x (xx.x%)	x (xx.x%)	x (xx.x%)	x (xx.x%)
Asian	x (xx.x%)	x (xx.x%)	x (xx.x%)	x (xx.x%)
Black or African American	x (xx.x%)	x (xx.x%)	x (xx.x%)	x (xx.x%)
Native Hawaiian or Other Pacific Islander	x (xx.x%)	x (xx.x%)	x (xx.x%)	x (xx.x%)
White	x (xx.x%)	x (xx.x%)	x (xx.x%)	x (xx.x%)
Other	x (xx.x%)	x (xx.x%)	x (xx.x%)	x (xx.x%)
Ethnicity				
Hispanic or Latino	x (xx.x%)	x (xx.x%)	x (xx.x%)	x (xx.x%)
Not Hispanic or Latino	x (xx.x%)	x (xx.x%)	x (xx.x%)	x (xx.x%)
Not Reported	x (xx.x%)	x (xx.x%)	x (xx.x%)	x (xx.x%)
Unknown	x (xx.x%)	x (xx.x%)	x (xx.x%)	x (xx.x%)

Baseline is the last non-missing value prior to first dose of study treatment. Reference: Listing 16.2.4.1

Table 14.1.2

Demographic and Baseline Characteristics
(ITT Population)

Characteristic	GLS-1027	GLS-1027		
	120 mg	360 mg	Placebo	Overall
	(N=XX)	(N=XX)	(N=XX)	(N=XX)
Height (cm)				
n	XX	XX	XX	xx
Mean (SD)	xx.x (x.xx)	xx.x (x.xx)	xx.x (x.xx)	xx.x (x.xx)
Median	xx.x	xx.x	xx.x	xx.x
Min, Max	XX, XX	XX, XX	xx, xx	xx, xx
leight (kg)				
n	xx	XX	xx	XX
Mean (SD)	xx.x (x.xx)	xx.x(x.xx)	xx.x(x.xx)	xx.x(x.xx)
Median	xx.x	xx.x	xx.x	xx.x
Min, Max	XX, XX	XX, XX	xx, xx	xx, xx
BMI (kg/m^2)				
n	XX	xx	xx	xx
Mean (SD)	xx.x (x.xx)	xx.x(x.xx)	xx.x(x.xx)	xx.x(x.xx)
Median	xx.x	xx.x	xx.x	xx.x
Min, Max	xx, xx	XX, XX	xx, xx	xx, xx

BMI = Body Mass Index

Baseline is the last non-missing value prior to first dose of study treatment. Note: Body mass index (BMI) calculated as weight (kg) / [[height (cm)/100]²]. Reference: Listing 16.2.4.1

Table 14.1.3 Medical History (ITT Population)

System Organ Class Preferred Term	GLS-1027 120 mg (N=XX)	GLS-1027 360 mg (N=XX)	Placebo (N=XX)	Overall (N=XX)
Subjects with at least one medical history event	x (xx.x%)	x (xx.x%)	x (xx.x%)	x (xx.x%)
<pre><system #1="" class="" organ=""></system></pre>	x (xx.x%)	x (xx.x%)	x (xx.x%)	x (xx.x%)
<pre><preferred #1="" term=""></preferred></pre>	x (xx.x%)	x (xx.x%)	x (xx.x%)	x (xx.x%)
<preferred #2="" term=""></preferred>	x (xx.x%)	x (xx.x%)	x (xx.x%)	x (xx.x%)
System Organ Class #2>	x (xx.x%)	x (xx.x%)	x (xx.x%)	x (xx.x%)
<preferred #1="" term=""></preferred>	x (xx.x%)	x (xx.x%)	x (xx.x%)	x (xx.x%)
<preferred #2="" term=""></preferred>	x (xx.x%)	x (xx.x%)	x (xx.x%)	x (xx.x%)
•				
•				

MedDRA = Medical Dictionary for Regulatory Activities.

Medical history terms are coded using MedDRA version 23.0 and ordered by descending order of overall incidence of SOC and overall incidence of PT within each SOC. At each level of summation (overall, SOC, PT), subjects reporting more than one medical history term are counted only once. Reference: Listing 16.2.4.2

GeneOne Life Science Inc.

Page 1 of x

Protocol: GLS27-005

Table 14.1.4
Prior and Concomitant Medications
(ITT Population)

ATC Class	GLS-1027	GLS-1027	Placebo
Preferred Name	120 mg	360 mg	(N=XX)
	(N=XX)	(N=XX)	
Subjects who received any prior or concomitant			
medications	x (xx.x%)	x (xx.x%)	x (xx.x%)
Subjects who received any prior or concomitant corticosteroids	x (xx.x%)	x (xx.x%)	x (xx.x%)
ATC Class # 1>	x (xx.x%)	x (xx.x%)	x (xx.x%)
<preferred #1="" name=""></preferred>	x (xx.x%)	x (xx.x%)	x (xx.x%)
<preferred #2="" name=""></preferred>	x (xx.x%)	x (xx.x%)	x (xx.x%)
<preferred #3="" name=""></preferred>	x (xx.x%)	x (xx.x%)	x (xx.x%)
<atc #="" 2="" class=""></atc>	x (xx.x%)	x (xx.x%)	x (xx.x%)
<preferred #1="" name=""></preferred>	x (xx.x%)	x (xx.x%)	x (xx.x%)
<preferred #2="" name=""></preferred>	x (xx.x%)	x (xx.x%)	x (xx.x%)
<preferred #3="" name=""></preferred>	x (xx.x%)	x (xx.x%)	x (xx.x%)
•	, ,	. ,	, ,
•			

A concomitant medication is any medication that was ongoing or started on or after the date of first dose. A prior medication is defined as a medication that was administered up to 4 months prior to time of enrollment.

Medications are coded using WHODrug Global (March 2020) and ordered by descending order of overall incidence of ATC class and overall incidence of preferred name within each class. At each level of summation (overall, ATC class, preferred name), subjects reporting more than one medication are counted only once.

Reference: Listing 16.2.4.3

Programming Note: Sort table by descending overall count of ATC class and descending overall count of preferred name within each class.

Table 14.1.5
Treatment Exposure

	(Cafaty Danulation)		
	(Safety Population)	CLC 1027	
	GLS-1027	GLS-1027	
	120 mg	360 mg (N=XX)	Placebo (N=XX)
	(N=XX)		
Duration of exposure (days) [1]			
n	XX	xx	XX
Mean (SD)	xx.x (xx.xx)	xx.x (xx.xx)	xx.x (xx.xx)
Median	xx.x	xx.x	xx.x
Min, Max	xx, xx	XX, XX	XX, XX
Total number of doses taken			
n	XX	xx	XX
Mean (SD)	xx.x (xx.xx)	xx.x (xx.xx)	xx.x (xx.xx)
Median	XX.X	xx.x	xx.x
Min, Max	xx, xx	xx, xx	xx, xx
Total number of doses missed			
n	XX	xx	XX
Mean (SD)	xx.x (xx.xx)	xx.x (xx.xx)	xx.x (xx.xx)
Median	xx.x	xx.x	xx.x
Min, Max	xx, xx	xx, xx	XX, XX

^[1] Duration of exposure is defined as the date of last dose minus the date of first dose + 1. Reference: Listing 16.2.5.1.

Table 14.2.1.1

Analysis of Overall Treatment Failure
(ITT Population)

Overall/Subjects with prior or concomitant corticosteroids/Subjects without prior or concomitant corticosteroids

	GLS-1027	GLS-1027	Placebo (N=XX)	
	120 mg	360 mg		
	(N=XX)	(N=XX)		
Treatment Failure [1]	x (xx.x%)	x (xx.x%)	x (xx.x%)	
Achieved WHO level >=6	x (xx.x%)	x (xx.x%)	x (xx.x%)	
Lost to follow-up	x (xx.x%)	x (xx.x%)	x (xx.x%)	
Withdrawal of informed consent	x (xx.x%)	x (xx.x%)	x (xx.x%)	
Required salvage therapy	x (xx.x%)	x (xx.x%)	x (xx.x%)	
Discontinued study drug prior to discharge	x (xx.x%)	x (xx.x%)	x (xx.x%)	
Had missing assessment of WHO level classification	x (xx.x%)	x (xx.x%)	x (xx.x%)	
p-value [2]	0.xxxx	0.xxxx	, ,	
Maximum WHO Level = 6 (Intubation or Mechanical Ventilation)	x (xx.x%)	x (xx.x%)	x (xx.x%)	
Maximum WHO Level = 7 (Requirement for ECMO)	x (xx.x%)	x (xx.x%)	x (xx.x%)	
Maximum WHO Level = 8 (Death)	x (xx.x%)	x (xx.x%)	x (xx.x%)	

^[1] Subjects who met any of the reasons listed are considered treatment failures. Subjects who failed treatment for multiple reasons are counted once for each reason.

Reference: Listing 16.2.6.1

Programming note: Repeat for Table 14.2.1.2 Analysis of Overall Treatment Failure (mITT Population).

Programming note: Repeat for Table 14.2.1.3 Analysis of Overall Treatment Failure (PP Population).

Programming note: P-values will not be provided for corticosteroid use/non-use subset pages.

^[2] P-value is calculated using a Fisher's exact test and compares the active treatment to placebo. Will only be provided for the 120 mg group if the 360 mg group is significant.

GeneOne Life Science Inc.

Page 1 of 1

Protocol: GLS27-005

Table 14.2.2.1.1

Summary of the Number of Days Requiring ICU Care
(ITT Population)

	GLS-1027	GLS-1027	Placebo
	120 mg	360 mg	(N=XX)
	(N=XX)	(N=XX)	, ,
umber of Days Requiring ICU Care			
n	X	X	Х
Mean (SD)	xx.xx (xx.xxx)	xx.xx (xx.xxx)	xx.xx (xx.xxx)
Median	x.xx	x.xx	x.xx
nearan			xx.x, xx.x

Reference: Listing xxxxx

Programming note: Repeat for Table 14.2.2.1.2 Summary of the Number of Days Requiring ICU Care (PP Population).

Protocol: GLS27-005

Table 14.2.2.2.1

Summary of the Number of Days on Mechanical Ventilation
(ITT Population)

	GLS-1027	GLS-1027	Placebo
	120 mg	360 mg	(N=XX)
	(N=XX)	(N=XX)	, ,
umber of Days on Mechanical Ventilation			
umber of Days on Mechanical Ventilation n	х	x	×
	x xx.xx (xx.xxx)	x xx.xx (xx.xxx)	x xx.xx (xx.xxx)
n			

Reference: Listing 16.2.6.2

Programming note: Repeat for Table 14.2.2.2.2 Summary of the Number of Days on Mechanical Ventilation (PP Population).

Protocol: GLS27-005

Table 14.2.2.3.1 Summary of the Number of Days Requiring Nasal Oxygen (O_2) Administration (ITT Population)

	GLS-1027	GLS-1027	Placebo
	120 mg	360 mg	(N=XX)
	(N=XX)	(N=XX)	
umber of Days Requiring Nasal Oxygen (O2)			
umber of Days Requiring Nasal Oxygen (O_2)	x	x	x
	x xx.xx (xx.xxx)	x xx.xx (xx.xxx)	x xx.xx (xx.xxx)
n			

Reference: Listing 16.2.6.3

Programming note: Repeat for Table 14.2.2.3.2 Summary of the Number of Days Requiring Nasal Oxygen (O2) Administration (PP Population).

Protocol: GLS27-005

Table 14.2.2.4.1 Summary of the Number of Days Requiring CPAP Usage (ITT Population)

	GLS-1027	GLS-1027	Placebo
	120 mg	360 mg	(N=XX)
	(N=XX)	(N=XX)	, ,
umber of Days Requiring CPAP Usage			
n	X	x	Х
Mean (SD)	xx.xx (xx.xxx)	xx.xx (xx.xxx)	xx.xx (xx.xxx)
	x.xx	x.xx	x.xx
Median			

Reference: Listing 16.2.6.4

Programming note: Repeat for Table 14.2.2.4.2 Summary of the Number of Days Requiring CPAP Usage (PP Population).

Protocol: GLS27-005

Table 14.2.2.5.1

Summary of the Number of Days Requiring ECMO Administration (ITT Population)

	GLS-1027	GLS-1027	Placebo
	120 mg	360 mg	(N=XX)
	(N=XX)	(N=XX)	
umber of Days Requiring FCMO Administration			
	x	×	×
n	x xx.xx (xx.xxx)	x xx.xx (xx.xxx)	x xx.xx (xx.xxx)
umber of Days Requiring ECMO Administration n Mean (SD) Median			x xx.xx (xx.xxx) x.xx

Reference: Listing 16.2.6.5

Programming note: Repeat for Table 14.2.2.5.2 Summary of the Number of Days Requiring ECMO Administration (PP Population).

Protocol: GLS27-005

Table 14.2.2.6.1

Summary of the Number of Days with PEEP > 5 cm H20

(ITT Population)

	GLS-1027	GLS-1027	Placebo
	120 mg	360 mg	(N=XX)
	(N=XX)	(N=XX)	, ,
umber of Days with PEEP $>$ 5 cm H_2O			
	V	X	X
n	X	^	^
	xx.xx (xx.xxx)	xx.xx (xx.xxx)	xx.xx (xx.xxx)
n Mean (SD) Median			

Note: Only subjects who were intubated are included in this endpoint analysis.

Reference: Listing 16.2.6.2

Programming note: Repeat for Table 14.2.2.6.2 Summary of the Number of Days with PEEP > 5 cm H2O (PP Population).

Protocol: GLS27-005

Table 14.2.2.7.1 Summary of Maximal Levels of PEEP Values (ITT Population)

	GLS-1027	GLS-1027	Placebo
	120 mg	360 mg	(N=XX)
	(N=XX)	(N=XX)	
aximal Level of PEEP			
n	X	x	Х
Mean (SD)	xx.xx (xx.xxx)	xx.xx (xx.xxx)	xx.xx (xx.xxx)
Median	x.xx	x.xx	x.xx
Min, Max	XX.X, XX.X	xx.x, xx.x	xx.x, xx.x

Note: Only subjects who were intubated are included in this endpoint analysis.

Reference: Listing 16.2.6.2

Programming note: Repeat for Table 14.2.2.7.2 Summary of Maximal Levels of PEEP Values (PP Population).

Protocol: GLS27-005

Table 14.2.2.8.1
Summary of the Number of Days in Hospital
(ITT Population)

	GLS-1027	GLS-1027	Placebo
	120 mg	360 mg	(N=XX)
	(N=XX)	(N=XX)	· · ·
umber of Days in Hospital			
n	X	x	x
Mean (SD)	xx.xx (xx.xxx)	xx.xx (xx.xxx)	xx.xx (xx.xxx)
Median	x.xx	x.xx	x.xx
Min, Max	xx.x, xx.x	xx.x, xx.x	xx.x, xx.x

Reference: Listing xxxxx

Programming note: Repeat for Table 14.2.2.8.2 Summary of the Number of Days in Hospital (PP Population).

Table 14.2.3.1

Cumulative Incidence of SARS-CoV-2 IgM Antibody Response by Study Day

(PP Population)

Study Day	GLS-1027	GLS-1027	Placebo
Responded	120 mg	120 mg	(N=XX)
	(N=XX)	(N=XX)	`n(%)´
	,	· · · · · · · · · · · · · · · · · · ·	
Day 1			
n	X	X	X
Yes	x (xx.x%)	x (xx.x%)	x (xx.x%)
No	x (xx.x%)	x (xx.x%)	x (xx.x%)
Day 2			
n	X	x	Х
Yes	x (xx.x%)	x (xx.x%)	x (xx.x%)
No	x (xx.x%)	x (xx.x%)	x (xx.x%)
Day 3			
n	X	X	X
Yes	x (xx.x%)	x (xx.x%)	x (xx.x%)
No	x (xx.x%)	x (xx.x%)	x (xx.x%)
Day 4			
n	X	X	X
Yes	x (xx.x%)	x (xx.x%)	x (xx.x%)
No	x (xx.x%)	x (xx.x%)	x (xx.x%)
	(,	~ ()	. (,
••			

The incidence of antibody response is summarized based on results obtained at or prior to the study day. Reference: Listing 16.2.6.3

Table 14.2.4.1
WHO COVID-19 Classification Levels Relative to Baseline Serum Ferritin Level
(PP Population)

			GL	S-1027			GLS-1027								
				L20 mg			360 mg			Placebo			0verall		
WHO Classification	(N=XX)						(N=XX)			(N=XX)		(N=XX)			
Level	Serum Ferritin [1]	Post-Baseline					Post-Baseline			Post-Baseline			Post-Baseline		
	Baseline	Low	N	lormal	High	Low	Normal	High	Low	Normal	High	Low	Normal	High	
5	n	х		х	x	x	х	х	х	х	x	x	х	х	
	Low					XX	XX	XX	XX	XX	XX	XX	XX	XX	
		xx (xx	.x) xx	(xx.x) xx	(xx.x)	(xx.x)	(xx.x)	(xx.x)	(xx.x)	(xx.x)	(xx.x)	(xx.x)	(xx.x)	(xx.)	
	Normal					XX	XX	XX	XX	XX	XX	XX	XX	XX	
		xx (xx	.x) xx	(xx.x) xx	(xx.x)	(xx.x)	(xx.x)	(xx.x)	(xx.x)	(xx.x)	(xx.x)	(xx.x)	(xx.x)	(xx.	
	High					XX	XX	XX	XX	XX	XX	XX	XX	XX	
		xx (xx	.x) xx	(xx.x) xx	(xx.x)	(xx.x)	(xx.x)	(xx.x)	(xx.x)	(xx.x)	(xx.x)	(xx.x)	(xx.x)	(xx.	
6	n	х		х	x	x	х	х	х	х	x	x	х	х	
	Low					XX	XX	XX	XX	XX	XX	XX	XX	XX	
		xx (xx	.x) xx	(xx.x) xx	(xx.x)	(xx.x)	(xx.x)	(xx.x)	(xx.x)	(xx.x)	(xx.x)	(xx.x)	(xx.x)	(xx.	
	Normal					XX	XX	XX	XX	XX	XX	XX	XX	XX	
		xx (xx	.x) xx	(xx.x) xx	(xx.x)	(xx.x)	(xx.x)	(xx.x)	(xx.x)	(xx.x)	(xx.x)	(xx.x)	(xx.x)	(xx.	
	High					XX	XX	XX	XX	XX	XX	XX	XX	XX	
		xx (xx	.x) xx	(xx.x) xx	(xx.x)	(xx.x)	(xx.x)	(xx.x)	(xx.x)	(xx.x)	(xx.x)	(xx.x)	(xx.x)	(xx.	
7	n	х		х	x	x	x	х	х	х	x	x	х	х	
	Low					XX	XX	XX	XX	XX	XX	XX	xx	XX	
		xx (xx	.x) xx	(xx.x) xx	(xx.x)	(xx.x)	(xx.x)	(xx.x)	(xx.x)	(xx.x)	(xx.x)	(xx.x)	(xx.x)	(xx.	
	Normal					XX	XX	XX	XX	XX	XX	XX	XX	XX	
		xx (xx	.x) xx	(xx.x) xx	(xx.x)	(xx.x)	(xx.x)	(xx.x)	(xx.x)	(xx.x)	(xx.x)	(xx.x)	(xx.x)	(xx.	
	High					XX	XX	XX	XX	XX	XX	XX	XX	XX	
		xx (xx	.x) xx	(xx.x) xx	(xx.x)	(xx.x)	(xx.x)	(xx.x)	(xx.x)	(xx.x)	(xx.x)	(xx.x)	(xx.x)	(xx.	
8	n	х		х	x	x	x	х	х	х	х	х	x	х	
	Low					XX	XX	XX	XX	XX	XX	XX	XX	xx	
		xx (xx	.x) xx	(xx.x) xx	(xx.x)	(xx.x)	(xx.x)	(xx.x)	(xx.x)	(xx.x)	(xx.x)	(xx.x)	(xx.x)	(xx.	
	Normal					XX	XX	XX	XX	XX	XX	XX	XX	XX	
		xx (xx	.x) xx	(xx.x) xx	(xx.x)	(xx.x)	(xx.x)	(xx.x)	(xx.x)	(xx.x)	(xx.x)	(xx.x)	(xx.x)	(xx.	
	High					XX	XX	XX	XX	XX	XX	XX	XX	XX	
		xx (xx	.x) xx	(xx.x) xx	(xx.x)	(xx.x)	(xx.x)	(xx.x)	(xx.x)	(xx.x)	(xx.x)	(xx.x)	(xx.x)	(xx.	

^[1] Worst (most extreme) values presented for serum ferritin.

Reference: Listing xx.x.x.x

date time

Table 14.2.4.2 WHO COVID-19 Classification Levels Relative to Baseline Serum IL-6 Level (PP Population)

			GL	.S-1027			GLS-1027								
				.20 mg			360 mg			Placebo			Overall		
WHO Classification		(N=XX)					(N=XX)			(N=XX)			(N=XX)		
Level	Serum IL-6 [1]		Post-Baseline				Post-Baseline			Post-Baseline			Post-Baseline		
	Baseline	L	.ow N	lormal	High	Low	Normal	High	Low	Normal	High	Low	Normal	High	
5	n		x	x	x	x	x	x	x	x	x	x	x	х	
	Low					XX	XX	XX	XX	XX	XX	XX	XX	XX	
		xx (xx.x) xx	(xx.x) xx	(xx.x)	(xx.x)	(xx.x)	(xx.x)	(xx.x)	(xx.x)	(xx.x)	(xx.x)	(xx.x)	(xx.)	
	Normal					XX	XX	XX	XX	XX	XX	XX	XX	XX	
		xx (xx.x) xx	(xx.x) xx	(xx.x)	(xx.x)	(xx.x)	(xx.x)	(xx.x)	(xx.x)	(xx.x)	(xx.x)	(xx.x)	(xx.)	
	High					XX	XX	XX	XX	XX	XX	XX	xx	XX	
		xx (xx.x) xx	(xx.x) xx	(xx.x)	(xx.x)	(xx.x)	(xx.x)	(xx.x)	(xx.x)	(xx.x)	(xx.x)	(xx.x)	(xx.	
6	n		x	x	x	x	x	x	x	х	x	х	х	х	
	Low					XX	xx	XX	XX	XX	XX	XX	xx	XX	
		xx (xx.x) xx	(xx.x) xx	(xx.x)	(xx.x)	(xx.x)	(xx.x)	(xx.x)	(xx.x)	(xx.x)	(xx.x)	(xx.x)	(xx.	
Norm	Normal	,	•	` ,	` ,	XX	xx	XX	XX	XX	XX	XX	xx	` xx	
		xx (xx.x) xx	(xx.x) xx	(xx.x)	(xx.x)	(xx.x)	(xx.x)	(xx.x)	(xx.x)	(xx.x)	(xx.x)	(xx.x)	(xx.	
	High	`	,	` ,	, ,	XX	`xx´	XX	XX	XX	XX	XX	`xx´	` xx	
	G	xx (xx.x) xx	(xx.x) xx	(xx.x)	(xx.x)	(xx.x)	(xx.x)	(xx.x)	(xx.x)	(xx.x)	(xx.x)	(xx.x)	(xx.	
7	n		x	x	x	x	x	x	х	х	x	х	х	х	
	Low					XX	xx	XX	XX	XX	XX	XX	xx	xx	
		xx (xx.x) xx	(xx.x) xx	(xx.x)	(xx.x)	(xx.x)	(xx.x)	(xx.x)	(xx.x)	(xx.x)	(xx.x)	(xx.x)	(xx.	
	Normal	,	•		, ,	XX	xx	XX	XX	XX	XX	XX	xx	· xx	
		xx (xx.x) xx	(xx.x) xx	(xx.x)	(xx.x)	(xx.x)	(xx.x)	(xx.x)	(xx.x)	(xx.x)	(xx.x)	(xx.x)	(xx.	
	High	,	•		, ,	XX	xx	XX	XX	XX	XX	XX	xx	· xx	
	J	xx (xx.x) xx	(xx.x) xx	(xx.x)	(xx.x)	(xx.x)	(xx.x)	(xx.x)	(xx.x)	(xx.x)	(xx.x)	(xx.x)	(xx.	
8	n		x	x	×	х	x	x	x	x	x	x	x	x	
	Low					XX	XX	XX	XX	XX	XX	XX	XX	XX	
		xx (xx.x) xx	(xx.x)xx	(xx.x)	(xx.x)	(xx.x)	(xx.x)	(xx.x)	(xx.x)	(xx.x)	(xx.x)	(xx.x)	(xx.	
	Normal	,	•	•		xx	xx	XX	XX	XX	xx	XX	XX	· xx	
		xx (xx.x) xx	(xx.x) xx	(xx.x)	(xx.x)	(xx.x)	(xx.x)	(xx.x)	(xx.x)	(xx.x)	(xx.x)	(xx.x)	(xx.	
	High	,	•	•	. ,	xx	xx	xx	xx	xx	xx	xx	xx	` xx	
	Ŭ	xx (xx.x)xx	(xx.x) xx	((x x)	(xx x)	(xx.x)	(xx.x)	(xx.x)	(xx.x)	(xx.x)	(xx.x)	(xx.x)	(xx.	

^[1] Worst (most extreme) values presented for serum IL-6. Reference: Listing xx.x.x.x

date time

Table 14.2.4.3 WHO COVID-19 Classification Levels Relative to Baseline CRP (PP Population)

			GLS-1027			GLS-1027							
			120 mg			360 mg			Placebo			Overall	
WHO Classification	600 [4]	(N=XX)				(N=XX)			(N=XX)		(N=XX) Post-Baseline		
Level	CRP [1]		Post-Baseline				Post-Baseline			Post-Baseline			
	Baseline	Low	Normal	High	Low	Normal	High	Low	Normal	High	Low	Normal	High
5	n	х	х	x	x	x	x	x	x	х	х	х	х
	Low				XX	XX	XX	XX	XX	XX	XX	XX	XX
		xx (xx.x) xx (xx.x) x	x (xx.x)	(xx.x)	(xx.x)	(xx.x)	(xx.x)	(xx.x)	(xx.x)	(xx.x)	(xx.x)	(xx.)
	Normal				XX	XX	XX	XX	XX	XX	XX	XX	XX
		xx (xx.x) xx (xx.x) x	x (xx.x)	(xx.x)	(xx.x)	(xx.x)	(xx.x)	(xx.x)	(xx.x)	(xx.x)	(xx.x)	(xx.)
	High				XX	XX	XX	XX	XX	XX	XX	XX	XX
		xx (xx.x) xx (xx.x) x	x (xx.x)	(xx.x)	(xx.x)	(xx.x)	(xx.x)	(xx.x)	(xx.x)	(xx.x)	(xx.x)	(xx.)
6	n	х	х	x	х	x	х	x	x	х	х	x	х
	Low				XX	XX	XX	XX	XX	XX	XX	XX	XX
		xx (xx.x) xx (xx.x) x	x (xx.x)	(xx.x)	(xx.x)	(xx.x)	(xx.x)	(xx.x)	(xx.x)	(xx.x)	(xx.x)	(xx.)
	Normal				XX	XX	XX	XX	XX	XX	XX	XX	XX
		xx (xx.x) xx (xx.x) x	x (xx.x)	(xx.x)	(xx.x)	(xx.x)	(xx.x)	(xx.x)	(xx.x)	(xx.x)	(xx.x)	(xx.)
	High				XX	XX	XX	XX	XX	XX	XX	XX	XX
		xx (xx.x) xx (xx.x) x	x (xx.x)	(xx.x)	(xx.x)	(xx.x)	(xx.x)	(xx.x)	(xx.x)	(xx.x)	(xx.x)	(xx.)
7	n	х	X	x	x	x	x	x	x	х	х	x	х
	Low				XX	XX	XX	XX	XX	XX	XX	XX	xx
		xx (xx.x) xx (xx.x) x	x (xx.x)	(xx.x)	(xx.x)	(xx.x)	(xx.x)	(xx.x)	(xx.x)	(xx.x)	(xx.x)	(xx.)
	Normal				XX	xx	XX	XX	XX	XX	XX	xx	XX
		xx (xx.x) xx (xx.x) x	x (xx.x)	(xx.x)	(xx.x)	(xx.x)	(xx.x)	(xx.x)	(xx.x)	(xx.x)	(xx.x)	(xx.)
	High				XX	XX	XX	XX	XX	XX	XX	XX	XX
		xx (xx.x) xx (xx.x) x	x (xx.x)	(xx.x)	(xx.x)	(xx.x)	(xx.x)	(xx.x)	(xx.x)	(xx.x)	(xx.x)	(xx.)
8	n	x	x	х	x	x	x	x	x	x	x	x	х
	Low				XX	XX	XX	XX	XX	XX	XX	XX	xx
		xx (xx.x) xx (xx.x) x	x (xx.x)	(xx.x)	(xx.x)	(xx.x)	(xx.x)	(xx.x)	(xx.x)	(xx.x)	(xx.x)	(xx.)
